APPENDIX 2 LEVODOPA EQUIVALENT ALGORITHM

Rules for Levodopa Equivalent

a) Ignore carbidopa – carbidopa does not go into the calculation of LevoEq.

Steps:

1. Calculate total immediate release daily Levodopa (note: there are combination drugs containing levodopa and you must separate these out and include in your calculation of daily Levodopa) by multiplying the mg per dose of levodopa by dosing frequency (BID=2, TID=3, QD=4, etc.)
2. Calculate total control release daily Levodopa. Multiply this by 0.75 (to account for loss of bioavailability)
3. Calculate total extended release Levodopa (i.e., Rytary). Multiply this by .60.
4. Add 1) and 2) and 3) to get total daily Levodopa
5. If Entacapone is taken (including combination drugs with Entacapone, i.e., Stalevo), multiply total daily Levodopa in 4) by 0.33.
6. If Tolcapone is taken, multiply total daily Levodopa in 3) by 0.5
7. If Duodopa is taken, multiply the daily mg by 1.11
8. If Pramipexole (as salt) is taken, multiply the daily mg by 100
9. If Ropinirole or RequipXL is taken, multiply the daily mg by 20
10. If Rotigotine is taken, multiply the daily mg by 30
11. If Selegiline – oral is taken, multiply the daily mg by 10
12. If Selegiline – sublingual is taken, multiply the daily mg by 80
13. If Rasagiline is taken, multiply the daily mg by 100
14. If Amantadine is taken, multiply the daily mg by 1
15. If Apomorphine is taken, multiply the daily mg by 10
16. Calculate total LevoEq = 4) + 5) + 6) + 7) + 8) + 9) + 10) + 11) + 12) + 13) + 14) + 15)

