4.0 SELECTION AND WITHDRAWAL OF PATIENTS

4.1 Inclusion Criteria

Patients must fulfill all of the following inclusion criteria in order to be included in the study:

1. Patient is informed and given ample time and opportunity to think about his/her participation in this study and has given his/her written informed consent on an Independent Ethics Committee (IEC) or Institutional Review Board (IRB) approved consent form.
2. Patient is considered reliable and capable of adhering to the protocol (e.g., able to understand and complete diaries), visit schedule, and medication administration instructions according to the judgment of the investigator.
3. Patient has a documented history of idiopathic Parkinson's disease consistent with the UK Parkinson's Disease Society Brain Bank Diagnostic criteria prior to the Screening Visit.
4. Patient has a PD duration of at least 3 years from diagnosis.
5. Patient has a modified Hoehn and Yahr stage 2–4 when in OFF state (estimated) and ≤ 3 in ON state.
6. Patient is male or female and 30–80 years old (inclusive) at Screening.
7. Patient must have a good response to levodopa in the opinion of the investigator, be taking at least four doses of a levodopa-containing medication per day, and at least one other concomitant anti-PD medication (dopamine agonists, MAO-B inhibitors, anticholinergic agents, amantadine or entacapone).
8. Patient is maintained on a regimen of permitted anti-PD medications that has been stable for at least 4 weeks prior to Screening.
9. Patients must have been taking a levodopa-containing anti-PD medication continuously for at least the previous 12 months and must be currently experiencing end-of-dose “wearing-off” with at least 2.5 hours of OFF time per day as confirmed by a 3-day Baseline diary.

10. Patient must have achieved the following results for PD diary training, practice diary collection, and Baseline diary recordings:

- a. During a diary concordance session with an approved PD diary trainer/rater (minimum 2.5 hours), patient achieved at least 80% overall diary concordance including at least 1 OFF interval.
- b. Returned a valid 3-day (i.e., 3 consecutive 24-hour periods) practice diary.
- c. Returned valid diary recordings for each of the 3 consecutive days preceding the Baseline Visit that indicated at least 2.5 hours of OFF time on each of the 3 days.

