9.3.3.2. Total Levodopa Equivalents

The total levodopa equivalent at baseline and during the study will be calculated for each subject at each visit and summarized descriptively for each visit in the FAS. A separate listing will also be created listing each subject's calculated total levodopa equivalent by visit. [Appendix 2](#) contains the rules to calculate levodopa equivalents.

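### Step 1 of the levodopa-equivalent algorithm codes QD as 4, so a once-daily immediate-release levodopa record would be counted at four times its dose

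*SAP*

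**What the plan says.** SAP 9.3.3.2 plans a descriptive summary of total levodopa equivalents at each visit in the FAS and states that Appendix 2 "contains the rules to calculate levodopa equivalents". SAP 5.10.2 also sends the reader there for the baseline value. The appendix is therefore the working specification for this variable.

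Step 1 of the appendix opens with "Calculate total immediate release daily Levodopa", which includes the levodopa part of combination products. The operation is "by multiplying the mg per dose of levodopa by dosing frequency", and the key supplied is "by dosing frequency (BID=2, TID=3, QD=4, etc". QID does not appear, and neither document defines QD.

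The later steps are worded differently. Step 2 reads "Calculate total control release daily Levodopa. Multiply this by 0.75", and step 3 treats extended-release levodopa in the same way with a factor of 0.60; neither restates the frequency key. Step 4 adds steps 1 to 3. For entacapone, step 5 says "multiply total daily Levodopa in 4) by 0.33", and step 16 adds that product to the total. Steps 7 to 15 start from the daily milligrams of each drug, for example "If Rasagiline is taken, multiply the daily mg by 100".

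In the main text, SAP 5.10.1 defines baseline total daily levodopa as dose times number of tablets times daily frequency. Protocol 4.1, inclusion criterion 7, requires a patient to "be taking at least four doses of a levodopa-containing medication per day".

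**The concern.** The key gives the once-daily code the multiplier that belongs to four times daily. It also leaves four times daily without its usual code, although inclusion criterion 7 makes that an expected levodopa schedule. A programmer who applies step 1 as written multiplies a QD immediate-release record by 4. One who follows 5.10.1 multiplies it by 1. The SAP thus gives two answers for the same record.

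Background anti-PD drugs may be adjusted throughout this open-label study (Protocol 5.9.1). Levodopa equivalents by visit are one of the SAP's quantitative summaries of those adjustments, and readers will set the UPDRS and diary summaries against them. If a QD levodopa line starts, stops or changes dose between visits, the summary would show four times the true change.

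**Working it through.** The SAP gives no worked levodopa-equivalent total, so there is no stated result to reproduce. The check is direct arithmetic on the steps. **All doses below are illustrative assumptions.** The multipliers and factors come from Appendix 2.

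**1. A single QD record of immediate-release levodopa.** Daily levodopa = mg per dose × frequency code.

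| mg per dose | As written (QD=4) | Once daily (QD=1) | Excess |
|---|---|---|---|
| 50 | 200 | 50 | 150 |
| 100 | 400 | 100 | 300 |
| 200 | 800 | 200 | 600 |
| 250 | 1000 | 250 | 750 |

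The ratio is 4.0 in every row. The right-hand result is also what 5.10.1 gives, because its frequency term is 1 for once daily.

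**2. Carry-forward with entacapone.** Step 5 adds 0.33 × step 4, so the excess is multiplied by 1 + 0.33 = 1.33. For the 100 mg record, 300 × 1.33 = 399 mg/day.

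**3. A patient who meets inclusion criterion 7.** Take 100 mg four times daily (100 × 4 = 400 mg/day) plus one QD line.

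- 50 mg QD: 400 + 200 = 600 as written, against 400 + 50 = 450 (+33%).
- 100 mg QD: 400 + 400 = 800 as written, against 400 + 100 = 500 (+60%).
- 200 mg QD: 400 + 800 = 1200 as written, against 400 + 200 = 600 (+100%).

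If the 100 mg line were added between two visits, the apparent increase would be 800 − 400 = 400 mg/day, against a true 500 − 400 = 100 mg/day.

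**4. Doses entered line by line.** If four daily 100 mg doses were each recorded as a QD line, the total would be 4 × 100 × 4 = 1600 mg/day, against 4 × 100 = 400.

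**5. Drugs in steps 7 to 15.** These take daily milligrams × factor, with no frequency code. Rasagiline 1 mg once daily gives 1 × 100 = 100 and ropinirole 8 mg once daily gives 8 × 20 = 160, before and after the correction.

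**The case against.** The best case for leaving the point alone is that the intended meaning is recoverable. The run 2, 3, 4 indicates QID, inclusion criterion 7 fits that reading, and 5.10.1 already states the right principle. A programmer who reads the entry as QID inflates nothing. The entry rule also limits exposure: a once-daily immediate-release line would normally be one among several. A stable miscoded line shifts a patient's level equally at every visit and creates no false trend. Levodopa equivalents are not among the safety, other or exploratory variables in SAP 4.1, 4.2 and 9.6.1. No formal tests are planned (SAP 9), and SAP 9.3.3 and 9.3.3.1 give other views of background treatment.

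Most of this stands, and it sets the severity. It does not remove the defect. Even on the QID reading, a true once-daily record has no code. The independent second programming in SAP 10 is only a partial safeguard, because both programmers would work from the same appendix and two literal implementations would agree.

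In the other direction, a reader might infer that every once-daily drug is quadrupled, with rasagiline 1 mg counted as 400 and ropinirole 8 mg as 640. The documents do not support that. The key is attached only to immediate-release levodopa, steps 7 to 15 use daily milligrams, and 5.10.2 likewise starts from each drug's total daily dose. A reader might also count 200 mg of once-daily controlled-release levodopa as 200 × 4 × 0.75 = 600 instead of 200 × 1 × 0.75 = 150. That requires the step 1 key to be used in building the step 2 total, which the text does not say.

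**Conclusion.** The point holds within limits. Step 1 of Appendix 2 is wrong as written: it codes QD as 4, gives no correct code for once daily, and conflicts with 5.10.1. Read literally, it multiplies a QD immediate-release levodopa record by four. For a 100 mg record the excess is 300 mg/day, or 399 mg/day with entacapone.

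The conclusion rests on QD having its standard meaning and on the key being applied literally. The reach is the levodopa-equivalent summaries and listings. The total levodopa dose summaries in 9.3.3.1 would be affected only if the same key were used there; that section does not cite Appendix 2. The number of QD immediate-release records cannot be determined from the documents, so the effect on any group mean cannot be estimated. A distorted trend over visits is possible only if such records start, stop or change dose, and nothing in the documents shows that they will.

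No test and no safety endpoint depends on this. Severity: minor.

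**What to change.** In Appendix 2, step 1, replace the key with QD=1, BID=2, TID=3, QID=4. State that it agrees with 5.10.1 and applies wherever a daily levodopa total is built from dose and frequency, including the totals that enter steps 2 and 3.

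As a small separate correction, step 6 (tolcapone) refers to the total daily levodopa in step 3, but step 3 covers extended-release levodopa only. It should refer to step 4, as step 5 does. The practical effect is slight, because tolcapone is prohibited during the study (Protocol 5.9.2).

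The cost is a one-line SAP edit for each correction. Neither needs new data collection or a change to the analyses.
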